## **Appendix 4. Approximate Equivalent Morphine Doses of Opioid Analgesics**

## **Common Opioid Analgesics**

Drug	Maximum Allowed Total Daily Dose	Relative potency to oral morphine	Half-Life
Morphine	30 mg	1	1.5 – 4 hrs
Hydrocodone (Vicodin, Lortab)	30 mg	1	3.8 – 4.5 hrs
Hydromorphone (Dilaudid)	7.5 mg	4	2.5 hrs
Meperidine (Demerol, Pethidine)	300 mg	0.1	3.2 – 3.7 hrs
Methadone (Dolophine, Methadose, Physeptone)	10 mg	3.0	23 hrs
Codeine (Paveral, Tylenol #2 and #3)	200 mg	0.15	2.5 – 3.5 hrs
Oxycodone [Roxicodone; Percocet, Tylox]	15 mg	~2	3.2 hrs
Tramadol [Ultram, Zydol; Zamadol, Ultracet, Tramal]	300 mg	~0.1	4.7 – 5.1 hrs

Sites should contact project team for acceptable alternative preparations and related data. References:

2. Twycross R. Pain relief in advanced cancer. Edinburgh: Churchill Livingstone, 1994.

#### Appendix 5. Rescue Therapy

Acetaminophen/ paracetamol is allowable as rescue medication if dosed no more than 2.6 gm/day for no more than 10 consecutive days. If a subject is already taking stable background doses of acetaminophen/ paracetamol, s/he may increase the dose up to 2.6 gm/day for up to 10 consecutive days for rescue purposes.

# The following paradigm should be used to determine appropriate opioid rescue therapy:

*For subjects who are NOT on stable, background opioid therapy:* any of the following single opioid agents may be given as rescue medication (with or without acetaminophen/ paracetamol) for no more than 10 consecutive days in the following total daily doses:

- 1. Hydrocodone (with or without acetaminophen/paracetamol), not to exceed 30 mg total daily dose.
- 2. Oxycodone (with or without acetaminophen/paracetamol), not to exceed 15 mg total daily dose.
- 3. Tramadol (with or without acetaminophen/paracetamol), not to exceed 300 mg total daily dose.

#### For subjects who ARE on stable, background opioid therapy:

- They may NOT add a second opioid agent for rescue;
- If their background medication is 1 of the 3 listed above, they may, within the above maximum total dosage limits, increase the dosage for up to 10 consecutive days for rescue purposes;
- If their background medication is a short-acting (half-life <5 hrs, Appendix 4) opioid that is not one of those listed above, they may increase the dosage for up to 10 consecutive days (up to a total daily dose which must not exceed the potency equivalent of 30 mg of orally-administered morphine [Appendix 4]) for rescue purposes;
- Sustained release opioid formulations (eg, OxyContin®, MS Contin®) and opioids with half lives greater than 5 hours (eg, methadone, propoxyphene) may NOT be USED for rescue medication.

Sustained release opioid formulations (eg, OxyContin®, MS Contin®) and opioids with half lives greater than 5 hours (eg, methadone, propoxyphene; see also Appendix 4) may NOT be INCREASED for rescue purposes.

Intravenous or intramuscular corticosteroids, biologic response modifiers and DMARDs, other than methotrexate and sulfasalazine, are not allowed during this study. Intra-articular corticosteroids may be given at or after the Month 3 visit in no more than two joints, in a cumulative dose of no more than 40 mg methylprednisolone or its equivalent in any 6 month study period. The total allowed intraarticular corticosteroid dose may be divided into separate injections (eg, 20 mg, 20 mg). Intra-articular hyaluronate sodium injections may be administered for indications in accordance with the local label at or after the Month 3 visit, intra-articular injections must be given after assessments are completed. Intra-articular corticosteroids should not be administered within 4 weeks prior to a study visit.

Acetaminophen/paracetamol is not permitted as a part of combination products such as over-the-counter "cold remedies" or in combination with opioids if the acetaminophen/paracetamol dose will exceed 2.6 gm/day. Subjects who require rescue for more than 10 consecutive days should be discontinued from the trial. In addition, subjects should not be dosed with rescue acetaminophen/paracetamol or opioids within 24 hours prior to a study visit. Baseline stable acetaminophen/paracetamol or opioids should NOT be discontinued in advance of study visits.

Subjects should not be dosed with any rescue intervention within 24 hours prior to a study visit unless medically necessary.

#### Appendix 6. Evaluation of Potentially Malignant Tumors, Suspicious Lymphadenopathy, Possible Extranodal Lymphoproliferative Disorder (LPD)

The following steps should be taken in the event of potentially malignant tumors, lymphadenopathy or possible extranodal lymphoproliferative disorder (LPD) which might arise in the course of this study.

When there is a decision to biopsy a potentially malignant tumor, lymph node, or other tissue, the investigator and/or consultants should contact the Pfizer study team to discuss the issue and any decisions as soon as possible. It is recommended that specialists with experience in the evaluation of immunosuppressed patients be consulted.

If a biopsy for lymphadenopathy or lymphoma is to be performed, the investigator or consultant should refer to the instructional slide deck in the Lymph Node Biopsy kit and review the following points with the surgeon and pathologist:

- Fine needle aspiration and core needle biopsy are strongly discouraged; excisional biopsy is required for accurate diagnosis;
- Tissue must be sent fresh to the pathology laboratory; the pathologist must be consulted before the procedure;
- Archive multiple frozen tissue samples, if possible;
- Include flow cytometry and cytogenetics as part of the pathologic evaluation;
- Culture for mycobacterium and fungi, if indicated;
- Collect and snap freeze peripheral blood lymphocytes for germ line evaluation (DNA);
- Archive multiple aliquots of serum samples.

For all biopsies, please request the pathologist to send the original slides used to make the definitive diagnosis, ancillary study reports, and the pathologist's report to the central laboratory.

## **1. VERSION HISTORY**

SAP Version	Associated Protocol Amendment	Change	Rationale
1 (17-APR-2018)	Protocol Amendment 1 (20-NOV-2017)	None	Not Applicable
2 (22-FEB-2021)	Protocol Amendment 4 (04-JUN-2020)	Sections 2.2 and 5.3: Protocol languages were updated	To be consistent with protocol amendment 4.
		Section 3.4.3: Added details for prior DMARDs use summaries.	To clarify how prior DMARDs use will be summarized.
		Section 4.2.1: Added one additional criterion for subject exclusion from Per- Protocol analysis set.	To exclude subjects with history of or current autoimmune rheumatic disease or rheumatic inflammatory disease other than PsA.
		Sections 5.2 and 5.2.1.1: Updated method for reporting response rate when the rate is 0 or 100%.	To clarify the reporting method.
		Section 6.1.1.2 and Appendix 1: Sensitivity analysis in the per-protocol analysis set is renamed a supportive analysis.	Sensitivity analysis is reserved for a different statistical method but otherwise everything else (including the analysis set and missing data handling method) stays the same.
		Sections 6.2.1 and 6.2.2: Line graph will	For TLF reduction.

## Table 1 Summary of Major Changes in SAP Amendments

	only be produced for selected endpoints.	
	Section 6.4: Updated specifications for subgroup analysis by baseline csDMARD use.	To clarify the categories in subgroup analysis by baseline csDMARD use.
Section 6.6.1: Analysis periods for AE display were updated.		For TLF reduction.
	Section 6.7: A new section was added for additional analyses to address COVID-19 pandemic impacts	To add additional analyses addressing COVID-19 pandemic impacts.
	Appendix 2: Added clarifications for definitions of visit windows in reporting.	To clarify visit window definition in special cases.
details in efficacy		To make sure data derivation will be programmed correctly.
	Appendix 4: Re- formatted the descriptions of tipping point analysis into a step-by-step format and pre-specified the number of multiple imputations and the	To make sure tipping point analysis will be programmed correctly.

	values of MNAR adjustment.	
	Other updates in Sections 3.2.1, 3.4, 4.2, 5.3, 6.2.1, Appendix 1 and Appendix 3.	Minor corrections and clarifications for consistency.

## **2. INTRODUCTION**

Psoriatic arthritis (PsA) is a chronic inflammatory autoimmune disease characterized by joint inflammation and destruction, psoriatic skin lesions, enthesitis, dactylitis, spondylitis, progressive disability and adverse effects on quality of life. Tofacitinib (CP-690,550) is a potent and selective inhibitor of the Janus Kinase (JAK) family of kinases. While tofacitinib shows nanomolar inhibitory potency against all JAK family kinases in enzymatic assays, it shows functional specificity for JAK1 and JAK1/3 over JAK2 in cell-based assays. The broad effects of JAK1/3 inhibition on multiple cytokine pathways provide the rationale for developing tofacitinib as treatment for PsA.

This is a 6-month Phase 3 study designed to evaluate the efficacy and safety of tofacitinib 5 mg BID as a treatment for PsA in Chinese subjects with active PsA who have had an inadequate response in their PsA to at least one conventional synthetic disease-modifying anti-rheumatic drug (csDMARD).

This SAP provides the detailed methodology for summary and statistical analyses of the data collected in study A3921234. This document may modify the plans outlined in the protocol; however, any major modifications of the primary endpoint definition or its analysis will also be reflected in a protocol amendment.

## 2.1. Study Objectives

#### 2.1.1. Primary Objectives

- To compare efficacy of tofacitinib 5 mg BID versus placebo for treatment of rheumatological signs and symptoms of PsA in Chinese subjects with active PsA who have had an inadequate response to at least one csDMARD.
- To compare the safety and tolerability of tofacitinib 5 mg BID versus placebo in Chinese subjects with active PsA who have had an inadequate response in PsA to at least one csDMARD.

### 2.1.2. Secondary Objectives

[figure not shown]
- To compare physical function status after administration of tofacitinib 5 mg BID versus placebo in Chinese subjects with active PsA who have had an inadequate response in PsA to at least one csDMARD.
- To compare the effects of tofacitinib 5 mg BID versus placebo on all health outcome measures in Chinese subjects with active PsA who have had an inadequate response to at least one csDMARD.
- To compare the efficacy of tofacitinib 5 mg BID versus placebo for the treatment of dermatological signs and symptoms of PsA in Chinese subjects who have had an inadequate response to at least one csDMARD.

## 2.2. Study Design

This is a Phase 3, randomized, 6-month, double-blind, placebo-controlled, parallel-group study designed to evaluate the efficacy and safety of tofacitinib in adult, Chinese subjects with active PsA who had an inadequate response in their PsA to at least one csDMARD. All subjects in the study will be evaluated for risk factors for venous thromboembolism. A total of approximately 204 subjects will be randomized in a 2:1 ratio to one of the following two parallel treatment sequences. The enrollment will be monitored to cap the proportion of subjects with baseline swollen joint count  $\leq 5$  at approximately 38% (i.e., approximately 78 subjects).

A schematic of the study design is shown in Figure 1.

#### Figure 1 Study Design

\*Primary study endpoints of ACR50 will be obtained at Month 3. All subjects randomized to placebo will receive tofacitinib 5 mg BID in a blinded manner after Month 3.

During the study, subjects are required to remain on a stable dose of one csDMARD, e.g., methotrexate or sulfasalazine, and should remain on that dose throughout the study.

# **3. ENDPOINTS AND BASELINE VARIABLES: DEFINITIONS AND CONVENTIONS**

Visual analog scale (VAS) data will need to be rescaled prior to any calculation and analysis. VAS is recorded on CRF in terms of length at mark (X in mm) and overall length of line (Y in mm). The rescaled VAS for use in analysis will be:  $Z=X/Y \times 100$  mm or  $X/Y \times 10$  cm, depending on endpoints or their use in defining other endpoints.

#### **3.1. Primary Endpoint(s)**

• ACR50 responder rate at Month 3.

#### **3.2. Secondary Endpoint(s)**

#### **3.2.1. Secondary Efficacy Endpoints**

- ACR20 and ACR70 responder rates at all timepoints;
- ACR50 responder rates at all timepoints other than Month 3 (Note that ACR50 responder rate at Month 3 is already mentioned as the primary endpoint);
- Change from baseline (Δ) in ACR response criteria components (HAQ-DI, C-reactive protein [CRP], Patient's Assessment of Arthritis Pain, Patient's Global Assessment of Arthritis, Physician's Global Assessment of Arthritis, swollen joint count, tender/painful joint count) at all timepoints;
- HAQ-DI response defined as a decrease from baseline ≥ 0.30 for subjects with baseline HAQ-DI ≥ 0.30 at all timepoints; HAQ-DI response defined as a decrease from baseline ≥ 0.35 for subjects with baseline HAQ-DI ≥ 0.35 at all timepoints;
- Psoriatic Arthritis Response Criteria (PsARC) at all timepoints;
- Physician's Global Assessment of Psoriasis (PGA-PsO) at Month 1, Month 3 and Month 6;
  - PGA-PsO response of clear or almost clear and a  $\geq$ 2-step improvement from baseline for subjects with baseline PGA-PsO  $\geq$  2;
  - $\Delta$ PGA-PsO for subjects with baseline PGA-PsO > 0;
- Psoriasis Area and Severity Index 75 (PASI75) response at Month 1, Month 3 and Month 6 for subjects with baseline psoriatic body surface area (BSA) ≥ 3% and baseline PASI > 0;

- Dactylitis severity score (DSS) at Month 1, Month 3 and Month 6 for subjects with baseline DSS > 0 (see Appendix 3 Section 12);
  - $\circ \Delta DSS;$
  - Resolution of dactylitis defined as a subject achieving DSS = 0;
- Enthesitis score [using Leeds enthesitis index (LEI)] at Month 1, Month 3 and Month 6 for subjects with baseline LEI > 0 (see Appendix 3 Section 11);
  - $\circ$   $\Delta LEI;$
  - Resolution of enthesitis defined as a subject LEI = 0;

#### **3.2.2.** Secondary Physical Function and Health Outcome Measures

Assessed at baseline, Months 1, 3 and 6:

• Short-Form-36 Health Survey ( $\Delta$ SF-36) Version 2, Acute;

This survey yields 10 endpoints: 8 general health domains: physical functioning, role limitations due to physical health, bodily pain, general health perceptions, vitality social functioning, role limitations due to emotional problems, and mental health. These domains can also be summarized as physical and mental component summary scores (PCS and MCS, respectively) (see Appendix 3 Section 6).

• EuroQol 5-Dimension Health State Profile - 3 Level Version ( $\Delta$ EQ-5D-3L).

This instrument yields 6 endpoints: scores from the five domains ( $\Delta$ EQ-5D) and an EQ-VAS score of the subject's health state today ( $\Delta$ EQ-VAS) (see Appendix 3 Section 7).

#### **3.3. Other Endpoints**

#### 3.3.1. Other Efficacy Endpoints

- $\Delta DAS28-3(CRP)$  at all timepoints;
- Physician's Global Assessment of Psoriatic Arthritis (ΔPGA-PsA) at Month 1, Month 3 and Month 6;
- Percent change from baseline (%∆) in PASI and PASI clinical sign component scores at Month 1, Month 3 and Month 6 for subjects with baseline BSA ≥ 3% and baseline PASI > 0;
- $\% \Delta BSA$  at Month 1, Month 3 and Month 6 for subjects with baseline BSA > 0%;
- Nail Psoriasis Severity Index (ΔNAPSI) Score at Month 1, Month 3 and Month 6 for subjects with baseline NAPSI > 0.

This is a score ranging from 0-8 based on 1 targeted nail.

Health Outcome Measures Assessed at baseline, Months 3 and 6:

 Work Productivity and Activity Impairment – Psoriatic Arthritis Questionnaire (ΔWPAI-PsA).

#### 3.4. Baseline Variables

#### 3.4.1. Demographic Characteristics

- Baseline age (2 categorizations: 18-44, 45-64, ≥ 65 years; 18-44, 45-64, 65-74, 75-84, ≥ 85 years; and continuous in years);
- Sex (female, male);
- Baseline body weight ( $< 60, \ge 60$  to  $\le 100, > 100$  kg; and continuous in kg),
- Baseline height (cm, continuous);
- Baseline Body Mass Index (BMI: < 18.5, 18.5 to < 25, 25 to < 30, 30 to < 40, and ≥ 40 kg/m^2; and continuous in kg/m^2);
- Screening smoking status (never smoked, former smoker, current smoker); smoking duration (years) for former and current smokers.
- Alcohol use [never, former, current; continuous (units/week) for subjects who consumed any alcohol].

#### **3.4.2.** Baseline Disease Characteristics

- PsA duration ( $< 2, \ge 2$  years; and continuous in years);
- Baseline PsA Subtype: (< 5 joints,  $\geq$  5 joints);
- Screening presence of distal interphalangeal joints involvement (yes, no);
- Screening presence of arthritis mutilans (yes, no);
- Baseline swollen joint count (66) (continuous);
- Baseline tender/painful joint count (68) (continuous);
- Baseline HAQ-DI (continuous);
- Baseline PGA-PsO (0, 1, 2, 3, 4);
- Baseline PGA-PsO (continuous) for those subjects with PGA-PsO > 0 at baseline;
- Baseline PASI  $(0, > 0 \text{ to } \le 20, > 20);$
- Baseline PASI (continuous) for those subjects with BSA ≥ 3% and PASI > 0 at baseline;
- Baseline total psoriatic BSA  $(0, > 0 \text{ to } < 3, \ge 3\%)$ ;

- Baseline total psoriatic BSA (continuous) for those with BSA > 0% at baseline,
- Number (%) of subjects with baseline PGA-PsO  $\geq$  3, PASI  $\geq$  12 and BSA  $\geq$  10%;
- Baseline presence of dactylitis (yes, no). Yes is defined for those subjects with baseline DSS > 0;
- Baseline DSS (continuous) for those subjects with DSS > 0 at baseline;
- Baseline presence of enthesitis measured by LEI (yes, no). Yes is defined for those subjects with baseline LEI > 0;
- Baseline enthesitis index measured by LEI (continuous) for those with LEI > 0 at baseline;
- Baseline SF-36 (8 domains, physical component score [PCS] and mental component score [MCS]);
- Baseline EQ-5D-3L (5 domains) and EQ-5D VAS;
- Baseline DAS28-3(CRP);
- Baseline CRP ( $\leq 2.87$ , > 2.87 mg/L; and continuous in mg/L);
- Baseline PGA-PsA;
- Baseline presence of nail psoriasis measured by NAPSI (yes, no). Yes is defined for those subjects with baseline NAPSI > 0;
- Baseline NAPSI for those with NAPSI>0 at baseline;
- Baseline diabetes mellitus (yes, no) (see Appendix 3 Section 14 for definition);
- Baseline metabolic syndrome (yes, no) (see Appendix 3 Section 15 for definition);
- Baseline cardiovascular risks;
- Baseline rheumatoid factor positive (yes, no);
- Baseline cyclic citrullinated peptide antibody positive (yes, no);

#### 3.4.3. Prior and Baseline Treatments for Psoriatic Arthritis

- Prior oral corticosteroids use (oral only: yes, no);
- Baseline oral corticosteroid use (oral only: yes, no), Day 1 predose;
- Prior NSAIDs use (yes, no);
- Baseline NSAID use (yes, no), Day 1 predose;
- Prior Other DMARDs use (yes, no). Other DMARDs are DMARDs other than bDMARDs and csDMARDs for primary diagnosis;

- Number of prior DMARDs experience (1 csDMARD, 2 csDMARDs, ≥ 3 csDMARDs, ≥ 1 bDMARD). This categorization is based on bDMARDs and csDMARDs experience, regardless of other DMARDs use. Subjects who were treated with any bDMARD or both csDMARDs and bDMARDs will be counted in the "≥ 1 bDMARD" category;
- Prior csDMARDs experience (yes for csDMARDs only, no). This categorization is based on bDMARDs and csDMARDs experience, regardless of other DMARDs use.

#### 3.5. Safety Endpoints

- Incidence and severity of adverse events (AEs);
- AEs of special interest (see Appendix 3 Section 13);
- Clinical laboratory tests (e.g., clinical chemistry, hematology);
- Vital sign measurements (blood pressure, pulse rate and temperature);
- Physical examinations;
- Electro-cardiogram (ECG) measurements.

#### 3.5.1. Adverse Events

An adverse event is considered treatment emergent relative to a given treatment if:

- the event occurs for the first time during the effective duration of treatment and was not seen prior to the start of treatment (for example, during the baseline or run-in period), or
- the event was seen prior to the start of treatment but increased in severity during treatment.

Any event occurring after the first day of the treatment will be attributed to the corresponding treatment period regardless whether the event occurs on- or off-treatment.

In addition to standard safety displays, a 3-tier approach will be used to summarize AEs. Under this approach, AEs are classified into 1 of 3 tiers. Different analyses will be performed for different tiers (See Section 6.6.1).

Tier-1 events: These are pre-specified events of clinical importance. The AEs of special interest (see Appendix 3 Section 13) are equivalent to Tier-1 events.

Tier-2 events: These are events that are not tier-1 but are "common". A MedDRA PT is defined as a tier-2 event if occurring in at least 4 subjects in any treatment group.

Tier-3 events: These are events that are neither tier-1 nor tier-2 events.

The 3 tiers are mutually exclusive. Tier-3 events will be included in standard safety displays and not separately displayed in specific Tier-3 tables.

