#### 5.1. Allocation to Treatment

#### **Study Treatments:**

Subjects are randomized to receive either tofacitinib 5 mg BID or placebo. At Month 3, all subjects receiving placebo will be advanced to tofacitinib 5 mg BID in a blinded manner for 3 months. Investigators, subjects and sponsor will remain blinded through the entire duration of the study until database release.

Subjects will be randomized in a 2:1 ratio to one of the following two parallel treatment sequences:

- **Treatment Sequence A**: Tofacitinib 5 mg BID;
- **Treatment Sequence B**: Placebo → Tofacitinib 5 mg BID at Month 3;

The following medication will be supplied by Pfizer Inc:

- Tofacitinib 5 mg tablets;
- Placebo tablets that match tofacitinib tablets.

Treatment Sequence	Treatment	Planned Number of Randomized Subjects
Sequence A	Tofacitinib 5 mg BID	136
Sequence B	Placebo x 3 Months $\rightarrow$ Tofacitinib 5 mg BID 	68

 At Month 3, subjects randomized into Treatment Sequence B will receive tofacitinib 5 mg BID in a blinded manner through Month 6.

Subjects will be randomized in a 2:1 ratio to Treatment Sequence A or Treatment Sequence B. Assignment to treatment sequence will be accomplished using an automated web/telephone randomization system (IVRS). The IVRS system contains the randomization schedule. At the Screening Visit, the investigative site will contact the IVRS (online or by telephone call). The site will enroll the subject into the IVRS by indicating minimal information sufficient to distinguish one subject from another (eg, date of birth and gender) and receive a unique subject identification number. At the Baseline/Day 1 (Visit 1), the system will associate that subject with the next available treatment on the randomization schedule and provide the randomization number. The system will then give the investigative site a code which corresponds to study drug that was previously shipped to the site and is in the site's inventory ready to be dispensed. This code corresponds to the study drug of that period in the treatment sequence in which the subject has just been randomized.

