#### 9.1. Sample Size Determination

The sample size and power analysis for the primary endpoint are based on the randomization of approximately 204 subjects in a 2:1 ratio. The sample size for this study is driven by the ACR50 response rate.

Assuming a placebo response rate of 9.5% and factoring in the number of subjects with primary endpoint missing due to COVID-19 (around 11 subjects as of 29 May 2020), a sample size of approximately 204 Chinese subjects (approximately 136 subjects in the tofacitinib treatment arm and 68 subjects in the placebo arm) randomized in a 2:1 ratio to tofacitinib and placebo arms will yield at least 90% power to detect a difference of 18.5% from placebo in ACR50 response rate, based on normal approximation (without continuity correction) at the 2-sided 5% significance level.

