## 5.2.3. Analyses of Tier-2 Adverse Events

Number and percentage of subjects with AEs over the first 3 months will be provided for each treatment group. Tier-2 events will be analyzed using asymptotic methods proposed by Miettinen and Nurminen (1985). Risk ratios (tofacitinib 5mg BID compared to placebo) and 2-sided 95% CI will be reported. P-values will not be reported for Tier-2 events.

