#### 6.6.1. Adverse Events

Data related to adverse events will be summarized descriptively through appropriate data tabulations, descriptive statistics, and graphical presentations:

- Incidence and severity of adverse events;
- Incidence of AEs of special interest;

- Serious infections will be summarized separately;
- Any safety events that trigger withdrawal of a subject;
- Special attention will be given to the events of anemia.

Adverse events will be reported as treatment-emergent all causality and treatment-emergent treatment-related. A treatment-emergent adverse event is any event that has: onset after the start of the first dose of study treatment, or onset prior to the first dose of study treatment and worsens in severity after the first dose of study treatment. The relationship of adverse event to study treatment is assigned by the investigator.

Adverse events will be displayed by two analysis periods: Baseline to Month 3 and Baseline to Month 6. Adverse events will be displayed from Baseline to Month 6 by treatment sequence groups and from Baseline to Month 3 by treatment groups.

In addition to the AE analyses described above, the AEs (all causality) are classified in 3 tiers and will be analyzed per the 3-tier approach. Below provides a brief summary.

Analysis of Tier-1 AEs (AEs of special interest) is covered above.

Tier-2 AEs will be analyzed per Section 5.2.3. No multiplicity adjustment will be used. Both tabular form and graphic (e.g., forest plots) display will be provided. They will be sorted by System Organ Class (SOC) and preferred terms (PT) within SOC, alphabetically, as well as by magnitude in risk ratio.

Tier-3 AEs will not be tabled separately but will be included in the standard AE analyses along with all other AEs.

It should be recognized that most studies are not designed to reliably demonstrate a causal relationship between the use of a pharmaceutical product and an adverse event or a group of adverse events. Except for select events in unique situations, studies do not employ formal adjudication procedures for the purpose of event classification. As such, safety analysis is generally considered as an exploratory analysis with the potential to generate hypotheses for further investigation. The 3-tier approach facilitates this exploratory analysis.

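### The Tier-2 adverse event rule applies one count of 4 subjects to arms of 136 and 68, which tilts the risk-ratio display towards apparent tofacitinib excesses for terms of about 1–4% incidence

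*SAP*

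**What the plan says.** SAP 3.5.1 sorts adverse events into three tiers. Tier 1 is the list of events of special interest. Tier 2 holds the remaining common terms: "A MedDRA PT is defined as a tier-2 event if occurring in at least 4 subjects in any treatment group". Everything else is Tier 3. The threshold is a raw count, the same for each group, and the sentence names no counting period.

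SAP 5.2.3 then says what Tier-2 status brings. The period is the first 3 months: "Number and percentage of subjects with AEs over the first 3 months will be provided for each treatment group". The statistic is a Miettinen–Nurminen comparison: "Risk ratios (tofacitinib 5mg BID compared to placebo) and 2-sided 95% CI will be reported". It adds: "P-values will not be reported for Tier-2 events". SAP 6.6.1 adds a plot ("Both tabular form and graphic (e.g., forest plots) display will be provided"), with terms sorted by system organ class and also by size of risk ratio. It makes no multiplicity adjustment and calls the safety analysis exploratory. Tier-3 terms stay in the standard adverse event tables but get no risk ratio, and Tier-1 events are summarized descriptively.

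The arms are unequal by design. Protocol 5.1 states: "Subjects will be randomized in a 2:1 ratio to Treatment Sequence A or Treatment Sequence B". Protocol 9.1 gives the sizes: "approximately 136 subjects in the tofacitinib treatment arm and 68 subjects in the placebo arm". Neither document adjusts the Tier-2 count for this allocation.

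**The concern.** Tier-2 status determines which preferred terms receive a tofacitinib-to-placebo risk ratio and a row in the forest plot. The rule selects on the same counts that the ratio then compares, and it uses one absolute bar for a large arm and a small one. A term reaches the bar through the tofacitinib arm at half the observed percentage that it would need through the placebo arm. For less frequent terms, a chance excess on tofacitinib therefore tends to be displayed, while a chance excess of the same size on placebo tends not to be.

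Safety and tolerability against placebo is one of the two primary objectives. A forest plot sorted by risk ratio is read for pattern and direction. If the selection rule supplies part of the direction, the reader cannot separate that part from a drug effect.

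**Working it through.** **Inputs.** The threshold is 4 subjects in any group (SAP 3.5.1). The total is about 204 at 2:1 (SAP 2.2), and the arm sizes are 136 and 68 (Protocol 9.1). The true incidence of a preferred term is not given in the documents. It is an assumption, varied from 1% to 8%.

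**Arm sizes.** 204 × 2/3 = 136 and 204 × 1/3 = 68, as the protocol states.

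**Threshold as a percentage.** 4/136 = 2.94% and 4/68 = 5.88%, a ratio of 2.0. For example, 4 v 0 subjects (2.9% v 0%) is Tier 2, but 0 v 3 (0% v 4.4%) and 2 v 3 (1.5% v 4.4%) are not.

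**Model.** Let A ~ Binomial(136, pT) and B ~ Binomial(68, pC), independent and enumerated exactly. The current rule selects a term if A ≥ 4 or B ≥ 4. Among selected terms, the direction is given by A/136 against B/68; ties make up the remainder.

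**Chance of reaching the bar in each arm, 2% in both.** P(A ≥ 4) = 29.0% and P(B ≥ 4) = 4.8%. P(selected) = 32.3%, and about 90% of selected terms have at least 4 subjects on tofacitinib.

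**Direction among selected terms, equal true incidence, current rule.**

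| Incidence in both arms | Selected | Tofacitinib higher | Placebo higher |
|---|---|---|---|
| 1% | 5% | 80% | 12% |
| 2% | 32% | 65% | 22% |
| 3% | 65% | 56% | 32% |
| 4% | 86% | 51% | 39% |
| 5% | 95% | 48% | 42% |
| 8% | 99.9% | 47% | 45% |

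The reference is not 50 v 50, because counts are discrete and allocation is 2:1. At 2% with no threshold (terms with at least one event), the split is 46% v 41%. The rule's own effect at 2% is therefore the move from 46/41 to 65/22. At 5% the no-threshold split is 47% v 44%, so almost nothing is due to the rule.

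**Share of events on tofacitinib.** Under equal incidence this should be 2/3. Among terms selected by the current rule it is 80% at 1% incidence and 73% at 2%.

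**Mirror-image true differences, chance of being displayed under the current rule.**

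| Higher v lower incidence | Higher on tofacitinib | Higher on placebo |
|---|---|---|
| 3% v 1% | 59% | 19% |
| 4% v 2% | 81% | 50% |
| 6% v 3% | 97% | 83% |
| 8% v 4% | 99.7% | 96% |

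**Alternative: A + B ≥ 4.** With equal incidence the split is 54% v 44% at 1% and 50% v 44% at 2%. The tofacitinib share of events is exactly 2/3 at every incidence, because selection depends only on the total. At 2%, 58% of terms qualify instead of 32%. For the 4% v 2% pair, display becomes 91% and 80%.

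**Alternative: proportional counts (A ≥ 4 or B ≥ 2, both 2.94%).** At 2% in both arms the tilt reverses, to 37% tofacitinib higher v 56% placebo higher, because the smaller arm is noisier. A cut-off of at least 3% in any arm (5/136 or 3/68) gives 44% v 55%.

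**The case against.** The strongest reply is that little depends on this. Tier-2 results carry no p-values, SAP 6.6.1 calls the safety analysis exploratory, the events of special interest are outside the rule, and no decision in the SAP rests on the forest plot. All of that stands, and it limits the point to a cheap improvement.

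Several stronger readings are tempting, and the documents do not support them:

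- *Terms with no drug effect appear mostly as ratios above 1.* This holds only at low incidence. At 5% the figure is 48%, and at 8% it is 47% v 45%. Tier 2 is meant for common events, and at 1% incidence only about 5% of terms qualify at all.
- *A placebo event needs twice the incidence to qualify.* This is true only of entry through the placebo count. A term can also enter on its tofacitinib count, and both arms are then shown. A 2% v 4% placebo excess is still displayed 50% of the time, and a 3% v 6% excess 83%.
- *Tier 2 is the only between-arm information on common harms.* It is the only planned risk-ratio display. Sub-threshold terms remain in the standard tables, which show adverse events to Month 3 by treatment group, so counts and percentages in both arms stay visible.
- *The rule conceals harm.* The tilt runs the other way: it over-displays apparent tofacitinib excesses.

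It is also fair to say that every threshold trades one imbalance for another. A percentage cut-off reverses the tilt for infrequent terms, and the pooled count leaves some asymmetry between mirror-image differences.

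**Conclusion.** The point holds within limits. One raw count applied to arms of 136 and 68 makes Tier-2 selection depend mainly on the tofacitinib count, and nothing elsewhere in the SAP corrects for this. Under equal true incidence the display tilts towards tofacitinib by 80% v 12% at 1%, 65% v 22% at 2% (46% v 41% with no threshold), 56% v 32% at 3% and 51% v 39% at 4%. From 5% upward the tilt is negligible. A true 4% v 2% excess on tofacitinib is displayed 81% of the time, and the same excess on placebo 50%.

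These figures rest on assumed incidences, on independent binomial counts and on the planned arm sizes. The safety set classifies subjects by treatment actually received, so the real denominators may differ slightly. The consequence is a directional distortion in an exploratory display. It does not hide a risk and does not affect any formal test.

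**What to change.** In SAP 3.5.1, define a Tier-2 event as a preferred term that is not Tier 1 and occurs in at least 4 subjects in the two treatment groups combined, from Baseline to Month 3. The stated period ties the count to the comparison in SAP 5.2.3. Any term with 4 subjects in one group has at least 4 in total, so every term that the current rule selects over that period is kept. The count needs no treatment codes, so it can be applied before unblinding.

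The cost is one sentence in the SAP, and a longer table and plot with some sparse rows and wide intervals (58% of terms qualifying instead of 32% at 2% incidence). The remaining mirror-image asymmetry (91% v 80% for 4% v 2%) should be accepted. If the sponsor prefers to keep the present rule, a note beside the forest plot should say that selection under 2:1 allocation favors terms with higher tofacitinib counts. A plain percentage cut-off should not be substituted, since it reverses the tilt for infrequent terms.
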